10.4.4 SAFETY ANALYSES

Safety, tolerability, and feasibility will be evaluated by examining the occurrence of AEs, including Treatment-Emergent AEs, and AEs leading to discontinuation from the study. AEs will be summarized by severity and by study drug dose.

Actual and changes from baseline in clinical laboratory measurements and vital signs will also be assessed and summarized. Abnormal values will be determined and flagged in the listings. Laboratory shift tables or graphics displaying the change (number of subjects) relative to the reference range from baseline to each study visit may also be presented for each test. The investigator should exercise his or her medical and scientific judgment in

deciding and documenting whether an abnormal laboratory finding, or other abnormal assessment is clinically significant.

Per-subject extent of exposure will be listed.

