2.3 Study Phase, Visit, and Day

The study is set up as shown above, along with assigned study period, visit, and day. In general, the baseline is defined as the last assessment before the first intake of the study medication unless otherwise specified. All scheduled assessments after first administration of study drug will be used.

Repeat/unscheduled assessments will not be used in descriptive statistics or any per-time point analyses but will be shown in listings as applicable. Pre-dose unscheduled assessments will be taken into account for baseline determination and post first dose unscheduled assessments will be taken into account for worst-case determination as applicable.

Reference date refers to the start date of the first study drug administration. All efficacy and safety assessments at all visits will be assigned a day relative to this date. The relative day will be defined as: visit date – reference date + 1 for visits on or after the reference date and visit date – reference date for visits before the reference date. Consequently, there is no 'Day 0' defined.

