6.2 Clinical Laboratory Evaluations

Numeric measurements of hematology, serum chemistry, urinalysis and urine chemistry will be investigated. Changes from baseline for all safety lab parameters will be summarized at each scheduled timepoint (Table 14.3.2.1.1-14.3.2.1.3). Frequency tables for categorical test results will be tabulated at each scheduled timepoint (Table 14.3.2.2). Shift tables from the baseline to each post-baseline scheduled timepoint will be presented (Table 14.3.2.3.1-14.3.2.3.3).

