6.4 Electrocardiogram

P-R interval, QT interval, QRS duration, Ventricular heart rate and QTc intervals using Bazett's correction formula and Fridericia's correction formula will be investigated. QTc values will be used as reported, they will not be recalculated. Changes from baseline for all Electrocardiogram (ECG) parameters will be summarized at each scheduled timepoint (Days 5, 85, and 89) (Table 14.3.4.1). In addition, frequency tabulation of the overall ECG results (Normal, Abnormal NCS, and Abnormal CS) will be summarized (Table 14.3.4.2).

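### The SAP reserves unscheduled post-dose results for a worst-case analysis, but no laboratory or ECG table makes one, so unscheduled values not reported as adverse events appear only in listings

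*SAP*

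**What the plan says.** SAP 2.3 sets three rules for results taken outside the schedule.

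- General exclusion: "Repeat/unscheduled assessments will not be used in descriptive statistics or any per-time point analyses but will be shown in listings as applicable".
- Before dosing: "Pre-dose unscheduled assessments will be taken into account for baseline determination".
- After dosing: "post first dose unscheduled assessments will be taken into account for worst-case determination as applicable".

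The SAP does not define the worst-case determination and does not mention it again.

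SAP 6.2 specifies three kinds of laboratory table. For changes: "Changes from baseline for all safety lab parameters will be summarized at each scheduled timepoint". For categories: "Frequency tables for categorical test results will be tabulated at each scheduled timepoint". For shifts: "Shift tables from the baseline to each post-baseline scheduled timepoint will be presented". Protocol 10.4.4 plans shifts on the same by-visit basis, as something that might be shown: "relative to the reference range from baseline to each study visit may also be presented for each test".

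For ECG, SAP 6.4 says "Changes from baseline for all Electrocardiogram (ECG) parameters will be summarized at each scheduled timepoint" and names Days 5, 85 and 89 (Table 14.3.4.1). It adds a frequency table of the overall reading (Table 14.3.4.2) without saying which tracings count. All laboratory and ECG results go to Listings 16.2.8.1 and 16.2.8.2.

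**The concern.** The plan names a use for unscheduled post-dose results, then provides no laboratory or ECG output in which that use occurs. The rule is also uneven: an unscheduled value before dosing can set the baseline of a shift, while an unscheduled value after dosing cannot be its end point.

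Safety is part of the primary objective, and change in laboratory parameters is a secondary safety endpoint (Protocol 3 and 4.2.2). A reader comparing the doses will want to know how many subjects were ever outside a limit. Rows by visit do not answer that, even for scheduled data. Reduced kidney function, defined as eGFR below 45 mL/min/1.73 m², is an adverse event of special interest (Protocol 8.4.3), yet SAP 6.2 specifies no count of subjects whose measured eGFR fell below that limit.

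**Working it through.** There is no stated figure to reproduce. The check compares the rule with the tables, then counts days between scheduled assessments.

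**1. Tables against the rule (SAP 6.2, 6.4 and 10)**

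| Output | Timing stated | Worst-case rule stated |
|---|---|---|
| 14.3.2.1.1 to 14.3.2.1.3, laboratory change (3 tables) | each scheduled timepoint | no |
| 14.3.2.2, laboratory categories (1 table) | each scheduled timepoint | no |
| 14.3.2.3.1 to 14.3.2.3.3, laboratory shift (3 tables) | each scheduled timepoint | no |
| 14.3.4.1, ECG change | Days 5, 85, 89 | no |
| 14.3.4.2, overall ECG result | none | no |

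The count is 0 of 3 + 1 + 3 = 7 laboratory tables and 0 of 2 ECG tables. SAP 2.6 treats frequency counts as descriptive summaries, so the exclusion in 2.3 covers Table 14.3.4.2 as well unless a worst-case rule is written for it.

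**2. Time during which any result is unscheduled (nominal days, Protocol 7.3 and 17)**

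- ECG after dosing starts: Days 5, 85 and 89. Gaps: 85 − 5 = 80 days, and 168 − 89 = 79 days to the end of study.
- Comprehensive or exit panel after dosing starts: Days 2, 4, 6, 56, 86, 88, 90, 140 and 168. Longest gaps: 56 − 6 = 50 and 140 − 90 = 50 days.
- Interim creatinine, BUN and eGFR on Days 28 and 112 shorten this for subjects who have them. The longest eGFR gap becomes 86 − 56 = 30 days. For creatinine and BUN it is 85 − 56 = 29 days, because the pre-infusion i-STAT on Day 85 measures both.
- Subjects randomized before 30 August 2018 have no interim laboratory tests, so the 50-day gaps remain for them. The documents do not give their number. The revision history for protocol version 5.0 mentions 24 subjects dosed. On the assumption that these are subjects of this trial, at least 24/40 = 60% of the planned sample is in this group.

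These gaps show when an unscheduled value could arise. They do not show how many will.

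**3. Rows by visit against subjects ever abnormal**

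Suppose, as an illustration, that six scheduled rows each show one abnormal subject of 40, or 1/40 = 2.5%. If it is the same subject each time, 1/40 = 2.5% were ever abnormal. If they are six different subjects, 6/40 = 15% were. The table is the same in both cases. This ambiguity concerns scheduled values and is separate from the loss of unscheduled ones; a worst-value count would resolve it.

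**4. The route through adverse events**

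Protocol 7.2.1 has the investigator decide whether an out-of-range laboratory value is clinically significant and requires those that are to be recorded as adverse events. Protocol 8.1.1 does the same for clinically significant new or worsened ECG findings. Protocol 8.4.3 makes eGFR below 45 an event of special interest. None of these is limited to scheduled visits, and SAP 6.1.5 tabulates both event types. What remains in listings only is the unscheduled number or category itself, and any abnormal unscheduled result not reported as an event.

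**5. What the sponsor did for blood pressure**

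SAP 8 explains that which blood pressures counted as events of special interest was left to the investigator, and that value ranges were therefore set for analysis. SAP 6.3 carries this out in Table 14.3.3.3, an incidence table based on measured values. There is no counterpart for eGFR, which also has a numeric limit. Entry required eGFR of at least 45 (Protocol 5.1), so a later value below 45 is normally a new crossing.

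**The case against.** A reader might infer that unscheduled results never reach a safety table. The documents do not support that: the adverse event route in step 4 carries the clinically important ones, from any visit, into the treatment-emergent and special-interest tables, and treatment-emergent events are the primary safety endpoint. This limits the point to values and to unreported abnormalities.

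A reader might also infer that the tables are biased towards normal, because extra samples tend to follow a worrying result. That is not shown. Protocol 7.1.1.1.10 gives one reason for repeating an ECG, which is to rule out artefact after an abnormal tracing. There, SAP 2.3 would summarize the suspect scheduled tracing and drop the repeat, so the error would run the other way. A simple worst-value rule would have the same fault.

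Other objections stand in part. Table 14.3.4.2 is silent on timing; it is not scheduled-only. The worst-case clause covers the whole SAP and is qualified, and blood pressure Table 14.3.3.3 is a natural place for it, so it is not empty everywhere. By-visit shifts follow the protocol. With about 40 subjects the listings can be read case by case, and the mock shells are a separate document that may say more. None of this gives a count of subjects ever abnormal by dose, and the SAP text should not leave its own rule to the shells.

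**Conclusion.** The point holds in a limited form. As written, the plan has no laboratory or ECG output for the worst-case use that it announces. Unscheduled values not reported as adverse events stay in listings, and the number of subjects ever abnormal by dose cannot be read from the tables. Reliance on the adverse event tables makes the eGFR result depend on investigator reporting, the dependence that led the sponsor to add a value-based table for blood pressure.

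The size and direction of any distortion are unknown, because no document gives the number of unscheduled samples. The intervals that can be counted are 80 and 79 days for ECG, and 50 days for the comprehensive panel. For eGFR the longest is about 30 days with interim tests and 50 days without. These rest on nominal visit days. The reading of the tables rests on the SAP text and table index alone. The change should be made before database lock.

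**What to change.** - **SAP 2.3:** define the worst-case determination for laboratory and ECG data, and make the exceptions below explicit.
- **SAP 6.2:** add to Tables 14.3.2.3.1 to 14.3.2.3.3 a shift from baseline to the worst post-baseline value, by dose and overall, using scheduled and unscheduled results. Where a test can be abnormal in both directions, show lowest and highest separately.
- **SAP 6.2:** add a count, by dose and overall, of subjects with any post-baseline eGFR below the protocol's own special-interest limit of 45, in the style of Table 14.3.3.3. The denominator is Safety Set subjects with at least one post-baseline value.
- **SAP 6.4:** define Table 14.3.4.2 as each scheduled visit plus worst post-baseline reading. State that a repeat done to rule out technical artefact replaces the suspect tracing in both.

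The cost is SAP wording, a few extra columns in existing tables and one short count. All the data are already collected. The downside is longer shift tables, since the added block repeats for every laboratory parameter.

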2.4 Analysis Sets

- Screened set (SCRN): All subjects who were screened and entered into EDC.
- Screen Failure set (SCRf): All subjects who were entered as screen failures in the EDC.
- Intention-to-Treat Dataset (ITT): All subjects who were randomized.
- Safety set (SAF): All subjects who received at least one dose of the study agent.
- Evaluable set (EVAL): All subjects who received at least 5 of the 10 planned doses.
- Per Protocol set (PPROT): A subset of the Evaluable set comprised of subjects who do not have any of the deviations listed below or any other deviation affecting efficacy identified prior to database lock.

Deviation Type	Deviation	Additional Clarification
Eligibility Inclusion Criteria Not Met	Diagnosis of probable AD based upon the National Institute on Aging-Alzheimer's Association (NIA-AA) Criteria	Subjects with a clinical diagnosis of AD according to NIA-AA criteria who have a negative amyloid PET scan will also be excluded.
Eligibility Inclusion Criteria Not Met	MMSE Score 12-24 inclusive	
Eligibility Inclusion Criteria Not Met	Modified Hachinski Ischemia Scale (MHIS) score of ≤ 4	
Eligibility Exclusion Criteria Met	Evidence of clinically relevant neurological disorder(s) other than AD	
Eligibility Exclusion Criteria Met	Initiation or change in the dosage of cholinesterase inhibitors (AChEI), memantine, Axona, vitamin E supplementation, or selegiline within 3 months prior to screening	Will be determined based upon actual date of change and proximity to screening. Will be determined prior to database lock
Eligibility Exclusion Criteria Met	Treatment with any human blood product, including transfusions and IV immunoglobulin, during the 6 months prior to screening	
Eligibility Exclusion Criteria Met	Concurrent daily treatment with benzodiazepines, long-acting opioids, or other medications that, in the investigator's opinion, interfere with cognition	
Eligibility Exclusion Criteria Met	Concurrent participation in another interventional clinical trial. Prior clinical trial subjects must have been off study agents for at least 30 days (or 5 half-lives, whichever is longer), 4 months for disease modifying therapies, and 1 year for vaccine or immunotherapy trials prior to screening.	

Deviation Type	Deviation	Additional Clarification
Eligibility Exclusion Criteria Met	A history of a major psychiatric disorder diagnosed before the onset of AD, including schizophrenia, major depression or bipolar disorder, and/or alcohol/substance dependency. Psychiatric symptoms that occur in the context of AD (e.g. psychosis, irritability, depression) are not exclusionary unless the PI believes they could interfere with study procedures	
Eligibility Exclusion Criteria Met	>2 lacunar strokes or other imaging abnormality on baseline MRI that would make the interpretation of subsequent MRI scans of the brain difficult.	Only if the MRI findings are indicative of another cause of dementia/cognitive impairment
Eligibility Exclusion Criteria Met	Any other condition and/or situation that the investigator believes may interfere with the safety of the subject, the intent and conduct of the study, or interpretation of study data	Only when interfering with the interpretation of study data
Compliance	Incorrect treatment dispensed and administered to subject	
Compliance	Received less than 5 doses	
Out of Window	Efficacy Procedures performed outside of the protocol window which are a consistent pattern or potential risk to study data outcomes	
Study Drug Temp Excursion	Study drug temperature excursions when determined to have impacted the quality of the study drug	
Concomitant meds	Use of prohibited concomitant medications as defined in the protocol that have an effect on cognition	

Decisions regarding which subjects are included in PPROT will be made before database lock.

A summary table of number (%) of patients in each analysis set and applicable treatment assignment will be provided (Table 14.1.1).

2.5 Definition of Subgroups

Subjects will be categorized into mild and moderate AD based on the baseline Mini-Mental State Examination (MMSE) with the recalculated total score >20 and ≤20, respectively.

2.6 Descriptive Summaries

All tabulated summaries will include the two treatment groups [REDACTED] and overall (includes data from both treatment groups). For endpoints that are continuous in nature: number of observations, mean, median, minimum and maximum, and standard deviation (SD) values will be presented as descriptive summary. For endpoints that are categorical in nature: frequency counts and percentages will be presented in the descriptive summary.

The number of decimal places to display for calculated data will be determined by the original scale of the data. Means, medians, and confidence intervals will be reported with one (1) additional decimal place. Standard deviation will be reported with two (2) additional decimal places. Minimum and maximum will be reported with the same number of significant digits as the method of capture.

For all efficacy and safety tables summarizing change from baseline, the baseline and post-baseline results at all planned timepoints will be included.

3 PLANNED INTERIM ANALYSIS

No interim analyses are planned.

4 SUBJECT INFORMATION

In general, all subject-level parameters will be summarized for the SAF set unless stated otherwise.

4.1 Disposition Information

Summaries will be provided for the following disposition information: Number of subjects screened, screening failures, randomized, completed study, discontinued study with the reasons of discontinuation from study, discontinued from study drug with the reasons of discontinuation from study drug, and discontinued from study but completed study drug dosing. The randomized treatment group will be shown for ITT set (Table 14.1.2).

4.2 Protocol Deviations

The number and percentage of subjects with protocol deviations will be tabulated per coded protocol deviation by severity (major vs minor) for the ITT set (Table 14.1.3.1).

The success of blinding will be assessed based on all occurrences (intentional or unintentional) of unblinding of blinded study subjects, their trial partners or study personnel (e.g. investigators, medical providers, cognitive testing raters, the Sponsor or their representatives) during infusions. Number of subjects with any occurrence of unblinding will be summarized on any day any period, any day each period, and each day within each period (Table 14.1.3.2).

4.3 Demographics and Baseline Characteristics

Descriptive statistics or frequency tabulation will be provided for the following parameters. The 'Declined to answer/don't know' will not be added for the denominator unless stated otherwise.

4.3.1 Demographic Parameters

Descriptive statistics or frequency tabulation will be provided for following parameters (Table 14.1.4.1):

- Age (years)
- Sex (Male, Female)
- Race (White, Black or African American, Asian, American Indian or Alaska Native, Native Hawaiian or Other Pacific Islander, Other Race, Multiple – derived if multiple races are checked)
- Ethnicity (Hispanic or Latino, Not Hispanic or Latino)
- Marital status (Single, Married, Widowed, Divorced/Separated)
- Family size
- Longest held career (Professional, Homemaker, Trade person, Arts/Entertainment)
- Annual household income ever reported (Less than \$50,000, \$50,000 to \$99,999, \$100,000 to \$199,999, \$200,000 or more).
- Weight at baseline (kg)
- Height at baseline (cm)
- Body Mass Index (BMI) at baseline = Weight at baseline (kg) / [Height at baseline (m)]² (rounded to 1 decimal. Although available in the raw data, BMI will be recalculated from last weight and height measurement before start of treatment)
- Duration of AD (years)
- Any Prior Treatments for AD (Yes/No)

4.3.2 Baseline Assessment of Modified Hachinski Ischemia Scale (MHIS)

No tabulation summary will be provided for MHIS data, which will be included in a subject data listing only.

4.3.3 Baseline Assessment of Columbia-Suicide Severity Rating Scale (C-SSRS)

The C-SSRS is a simple series of questions for the assessment of suicidal ideation and behavior in clinical trials (Posner 2011). The C-SSRS (including Actual Attempts Lethality) in both Lifetime and Last 6 Months are evaluated at screening visit.

Descriptive statistics or frequency tabulation will be provided for following C-SSRS parameters (Table 14.1.4.2):

- Suicidal Ideation (Yes/No): Wish to be Dead, Non-Specific Active Suicidal Thoughts, Active Suicidal Ideation without Intent to Act, Active Ideation with Some Intent without Specific Plan, Active Ideation with Specific Plan and Intent

- Intensity of Ideation
 - Most Severe Suicidal Ideation (1-5)
 - Frequency of Suicidal Ideation (1-5)
 - Duration of Suicidal Ideation (1-5)
 - Deterrents of Suicidal Ideation (0-5)
 - Controllability of Suicidal Ideation (0-5)
 - Reason of Suicidal Ideation (0-5)
- Suicidal Behavior:
 - Actual Attempt (Yes/No)
 - Total Number of Attempts
 - Interrupted Attempt (Yes/No)
 - Total Number of Interrupted Attempts
 - Aborted Attempt (Yes/No)
 - Total Number of Aborted Attempts
 - Preparatory Acts or Behavior (Yes/No)
 - Suicidal Behavior (Yes/No)
- Lethality - Most recent attempt:
 - Actual Lethality/Medical Damage (0-5)
 - Potential Lethality (0-2)
- Lethality - Most lethal attempt:
 - Actual Lethality/Medical Damage (0-5)
 - Potential Lethality (0-2)
- Lethality - Initial/First attempt:
 - Actual Lethality/Medical Damage (0-5)
 - Potential Lethality (0-2)

4.3.4 APOE Genotype

Frequency tabulation will be provided for APOE Genotype (E2/E2, E2/E3, E2/E4, E3/E3, E3/E4, E4/E4) (Table 14.1.4.3)

4.4 Medical History

The investigator or designee will obtain a detailed medical history through interview with the subject and the subject's trial partner during screening. The medical history should focus on duration of disease and recent history, with an emphasis on the history of cognitive symptoms related to probable AD.

Additionally, the medical history should include:

- Current/past illnesses and conditions
- Current symptoms
- Surgeries and procedures
- Allergies
- Family history
- Social history (e.g. exercise, smoking, alcohol, illegal substances) and current living situation
- Cause of parental death (if not living)

- Prior radiologic imaging, CSF assessments, and/or PET Scan results (if available and within 12 months of screening)

4.4.1 Subject Medical History

All reported subject medical history findings will be summarized by MedDRA system organ class and preferred term, in order of descending overall frequency (Table 14.1.5.1).

4.4.2 Family Medical History

All reported family medical histories will be listed by type of family member (Father, Mother, Brother, Sister, Son, Daughter, Half-Brother, Half-Sister) for following parameters:

- Status (Living, Deceased)
- Age at time of death (Years)
- History of neurological disease (Any, Alzheimer's, Parkinson's, Lewy body dementia, Frontotemporal dementia, Amyotrophic Lateral Sclerosis (ALS) or Lou Gehrig's disease, Vascular dementia, Other neurological Family Hx)

4.4.3 Social History

A frequency tabulation will be summarized for the following parameters (Table 14.1.5.2):

- Current Living Situation (In my home, In a relative or friend's home, In a care facility, Other, Declined to answer/don't know)
- Living conditions (Alone, With Family, With a Friend(s)/Roommate(s), With a Professional Caregiver, With One or More Pets, Declined to answer/don't know). Various living conditions will be arranged in order of descending overall frequency.

